6. DOSING DELAYS

Dose delays will be made as indicated in the following table(s). **No dose lowering/modifications will occur; only dose holds.** The descriptions and grading scales found in the revised NCI Common Terminology Criteria for Adverse Events (CTCAE) version 4.0 will be utilized for dose delays. A copy of the CTCAE version 4.0 can be downloaded from the CTEP website http://oten.comport.com/protocolDevelopment/alcotronic_applications/atc.htm

http://ctep.cancer.gov/protocolDevelopment/electronic applications/ctc.htm.

There will be no dose modifications for either pembrolizumab or Radium-223. Doses may be held for a maximum of 12 weeks for pembrolizumab and a maximum of 8 weeks for Radium-223 for resolution of toxicity. For delays longer than these intervals that are not due to toxicity of the agent and for which the patient was receiving clinical benefit, decisions to restart can be discussed with the PI and will be made on a case-bycase basis. The patient may be continued on either agent if one is discontinued and the other is not thought to be contributing to the toxicity in question.

Doses of either agent will not be omitted but can be given when the patient meets protocol specified criteria to treat. Interim reassessments between protocol specified dosing days are at the discretion of the treating physician.

Scans will stay on the same every 12 week (+/- 7 days) schedule even if doses are delayed.

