6.1 Dose Delay Guidelines for Pembrolizumab

Adverse events (both non-serious and serious) associated with pembrolizumab exposure may represent an immunologic etiology. These adverse events may occur shortly after the first dose or several months after the last dose of treatment. Pembrolizumab must be withheld for drug-related toxicities and severe or life-threatening AEs as per the Table below.

If an irAE is suspected, a thorough evaluation should be conducted in an effort to possibly rule out neoplastic, infectious, metabolic, toxin or other etiologic causes prior to diagnosing an irAE. Serological, immunological, and histological (biopsy) data should be considered to support the diagnosis of an immune-related toxicity.

Table 5: Summary of Dosing Guidelines for Drug-Related Adverse Events (see more detailed recommendations for each event below the table)

Toxicity	Hold Treatment For Grade	Timing for Restarting Treatment	Discontinue Subject
Diarrhea/Colitis	2-3	Toxicity resolves to Grade 0-1.	Toxicity does not resolve within 12 weeks of last dose or inability to reduce corticosteroid to 10 mg or less of prednisone or equivalen per day within 12 weeks.
	4	Permanently discontinue	Permanently discontinue
AST, ALT, or	2	Toxicity resolves to Grade 0-1	Toxicity does not resolve within 12 weeks of last dose.
Increased Bilirubin	3-4	Permanently discontinue	Permanently discontinue
Type 1 diabetes mellitus (if new onset) or Hyperglycemia	T1DM or 3-4	Hold pembrolizumab for new onset Type 1 diabetes mellitus or Grade 3-4 hyperglycemia	Resume pembrolizumab when patients are clinically and metabolically stable.
	2	Toxicity resolves to Grade 0-1	Toxicity does not resolve within 12 weeks of last dose or inability to reduce corticosteroid to 10 mg or less of prednisone or equivalen per day within 12 weeks.
Hypophysitis	3	Hold until toxicity resolves to Grade 0-1 or permanently discontinue per treating investigator's discretion	Hold until toxicity resolves to Grade 0-1 or permanently discontinue per treating investigator's discretion
	4 or Recurrent Grade 2 or 3	Permanently discontinue	Permanently discontinue
Hyperthyroidism	3	Toxicity resolves to Grade 0-1	Toxicity does not resolve within 12 weeks of last dose or inability to reduce corticosteroid to 10 mg or less of prednisone or equivalen per day within 12 weeks.
	4	Permanently discontinue	Permanently discontinue

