The following are considered events that should be reported to the Sponsor-Investigator within 24 hours of the site responsible investigator becoming aware of the event. The treatments are recommendations and the agents utilized should be determined by the treating clinician as deemed medically necessary.

Pneumonitis

The following AE terms, if considered \geq Grade 2, should be reported to the Sponsor-Investigator within 24 hours of the event:

- Pneumonitis
- Interstitial lung disease
- Acute interstitial pneumonitis

If symptoms indicate possible new or worsening cardiac abnormalities additional testing and/or a cardiology consultation should be considered. All attempts should be made to rule out other causes such as metastatic disease, bacterial or viral infection. It is **important that patients with a suspected diagnosis of pneumonitis be managed as per the guidance below until treatment-related pneumonitis is excluded. Treatment of both a potential infectious etiology and pneumonitis in parallel may be warranted. Management of the treatment of suspected pneumonitis with steroid treatment should not be delayed for a therapeutic trial of antibiotics.** If an alternative diagnosis is established, the patient does not require management as below; however, the AE should be reported to the Sponsor-Investigator regardless of etiology.

Course of Action

Grade 2 events:

- Report to Sponsor-Investigator
- Hold pembrolizumab.
- Consider pulmonary consultation with bronchoscopy and biopsy/BAL.
- Consider ID consult
- Conduct an in person evaluation approximately weekly
- Consider frequent Chest X-ray as part of monitoring

- Treat with systemic corticosteroids at a dose of 1 to 2 mg/kg/day prednisone or equivalent. When symptoms improve to Grade 1 or less, steroid taper should be started and continued over no less than 4 weeks.

- Permanently discontinue for inability to reduce corticosteroid dose to 10 mg or less of prednisone or equivalent per day within 12 weeks.

– Second episode of pneumonitis – discontinue pembrolizumab if upon re-challenge the patient develops a second episode of Grade 2 or higher pneumonitis.

Grade 3 and 4 events:

- Report to Sponsor-Investigator
- Discontinue pembrolizumab.
- Hospitalize patient
- Bronchoscopy with biopsy and/or BAL is recommended.

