- If symptoms worsen or persist > 3 days despite the above interventions, treat as Grade 3

Grade 3 Diarrhea/Colitis (or Grade 2 diarrhea that persists for > 1 week):

- Report to Sponsor-Investigator

- Hold pembrolizumab.

– Rule out bowel perforation. Imaging with plain films or CT can be useful.

- Recommend consultation with Gastroenterologist and confirmation biopsy with endoscopy.

- Treat with intravenous steroids (e.g., methylprednisolone 125 mg) followed by high dose oral steroids (e.g., prednisone 1 to 2 mg/kg once per day or dexamethasone 4 mg every 4 hours) When symptoms improve to Grade 1 or less, steroid taper should be started and continued over no less than 4 weeks. Taper over 6 to 8 weeks in patients with diffuse and severe ulceration and/or bleeding.

- Permanently discontinue for inability to reduce corticosteroid dose to 10 mg or less of prednisone or equivalent per day within 12 weeks.

- If IV steroids followed by high dose oral steroids does not reduce initial symptoms within 48 to 72 hours, consider treatment with additional anti-inflammatory measures (e.g., infliximab).

-Discontinue additional anti-inflammatory measures upon symptom relief and initiate a prolonged steroid taper over 45 to 60 days. If symptoms worsen during steroid reduction, initiate a re-tapering of steroids starting at a higher dose of 80 or 100 mg followed by a more prolonged taper and administer additional anti-inflammatory measures as needed.

Grade 4 events:

- Report to Sponsor-Investigator
- Permanently discontinue pembrolizumab.
- Manage as per Grade 3.

Endocrine

The following AE terms, if considered \geq Grade 3 or if \geq Grade 2 and require holding/discontinuation/modification of pembrolizumab dosing, should be reported to the Sponsor-Investigator within 24 hours of the event:

- Adrenal insufficiency
- Hyperthyroidism
- Hypophysitis
- Hypopituitarism
- Hypothyroidism
- Thyroid disorder
- Thyroiditis

All attempts should be made to rule out other causes such as brain metastases, sepsis and/or infection. However, the AE should be reported to the Sponsor-Investigator regardless of etiology.

Hypophysitis or other symptomatic endocrinopathy other than hypo- or hyperthyroidism

Grade 2-4 events:

- Report to Sponsor-Investigator if appropriate
- Hold pembrolizumab

- Rule out infection and sepsis with appropriate cultures and imaging.

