– Monitor thyroid function or other hormonal level tests and serum chemistries more frequently until returned to baseline values.

– Pituitary gland imaging should be considered (MRIs with gadolinium and selective cuts of the pituitary can show enlargement or heterogeneity and confirm the diagnosis).

- Treat with prednisone 40 mg p.o. or equivalent per day. When symptoms improve to Grade 1 or less, steroid taper should be started and continued over no less than 4 weeks. Replacement of appropriate hormones may be required as the steroid dose is tapered.

- Permanently discontinue for inability to reduce corticosteroid dose to 10 mg or less of prednisone or equivalent per day within 12 weeks.

- Hypophysitis with clinically significant adrenal insufficiency and hypotension, dehydration, and electrolyte abnormalities (such as hyponatremia and hyperkalemia) constitutes adrenal crisis.

- Consultation with an endocrinologist may be considered.

Hyperthyroidism and Hypothyroidism

Thyroid disorders can occur at any time during treatment. Monitor patients for changes in thyroid function (at the start of treatment, periodically during treatment, and as indicated based on clinical evaluation) and for clinical signs and symptoms of thyroid disorders.

Grade 2 hyperthyroidism, Grade 2-4 hypothyroidism events:

– Report to Sponsor-Investigator if appropriate (see Table 5)

- Monitor thyroid function or other hormonal level tests and serum chemistries more frequently until returned to baseline values.

- Thyroid hormone and/or steroid replacement therapy to manage adrenal insufficiency.

– Therapy with pembrolizumab can be continued while treatment for the thyroid disorder is instituted.

– In hyperthyroidism, non-selective beta-blockers (e.g. propranolol) are suggested as initial therapy.

– In hypothyroidism, thyroid hormone replacement therapy, with levothyroxine or liothyroinine, is indicated per standard of care.

- Consultation with an endocrinologist may be considered.

Grade 3 hyperthyroidism events:

– Report to Sponsor-Investigator

– Hold pembrolizumab.

– Rule out infection and sepsis with appropriate cultures and imaging.

- Treat with an initial dose of methylprednisolone 1 to 2 mg/kg intravenously followed by oral prednisone 1 to 2 mg/kg per day. When symptoms improve to Grade 1 or less, steroid taper should be started and continued over no less than 4 weeks. Replacement of appropriate hormones may be required as the steroid dose is tapered.

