- Permanently discontinue for inability to reduce corticosteroid dose to 10 mg or less of prednisone or equivalent per day within 12 weeks.

Grade 4 hyperthyroidism events:

- Report to Sponsor-Investigator

- Discontinue pembrolizumab.

– Manage as per Grade 3

Type 1 diabetes mellitus (if new onset) and ≥ Grade 3 Hyperglycemia

The following AE terms should be reported to the Sponsor-Investigator within 24 hours of the event:

Type I diabetes mellitus (T1DM), if new onset, including diabetic ketoacidosis (DKA)
Grade 3 or higher hyperglycemia, if associated with ketosis (ketonuria) or metabolic acidosis (DKA).

-Immune-mediated diabetes may present as new onset of Type 1 diabetes or an abrupt worsening of preexisting diabetes associated with laboratorial evidence of beta cell failure. All attempts should be made to rule out other causes such as type 2 diabetes mellitus (T2DM), T2DM decompensation, steroid-induced diabetes, physiologic stressinduced diabetes, or poorly controlled pre-existing diabetes (either T1DM or T2DM), but events meeting the above criteria should be reported to the Sponsor-Investigator regardless of etiology. The patients may present with hyperglycemia (abrupt onset or abrupt decompensation) with clinical evidence of diabetic ketoacidosis or laboratory evidence of insulin deficiency, such as ketonuria, laboratory evidence of metabolic acidosis, or low or undetected c-peptide.

Course of Action

T1DM or Grade 3-4 Hyperglycemia events:

- Report to Sponsor-Investigator if appropriate (see Table 5)

- Hold pembrolizumab for new onset Type 1 diabetes mellitus or Grade 3-4

hyperglycemia associated with evidence of beta cell failure, and resume pembrolizumab when patients are clinically and metabolically stable.

- Insulin replacement therapy is recommended for Type I diabetes mellitus and for Grade 3-4 hyperglycemia associated with metabolic acidosis or ketonuria.

- Evaluate patients with serum glucose and a metabolic panel, urine ketones, glycosylated hemoglobin, and C-peptide.

- Consultation with an Endocrinologist is recommended.

- Consider local testing for islet cell antibodies and antibodies to GAD, IA-2, ZnT8, and insulin may be obtained.

Hepatic

The following AE terms, if considered \geq Grade 2 or greater (or any grade with dose modification or use of systemic steroids to treat the AE), are considered Events of Clinical Interest (ECIs) and should be reported to the Sponsor-Investigator within 24 hours of the event:

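### Section 6.1 contradicts itself on grade 4 hypophysitis: Table 5 permanently stops pembrolizumab, while the event text only holds it

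*Combined protocol and SAP*

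**What the plan says.** Table 5 has three hypophysitis rows. Grade 2 is held until it resolves to grade 0-1. Grade 3 is held, or stopped for good at the investigator's discretion. The third row, "4 or Recurrent Grade 2 or 3", is a permanent stop in both the restart column and the discontinuation column.

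The event text below the table has a block for hypophysitis and other symptomatic endocrinopathy apart from thyroid disorders. It is headed "Grade 2-4 events" and tells the site to hold pembrolizumab. Its one stopping rule reads "Permanently discontinue for inability to reduce corticosteroid dose to 10 mg or less of prednisone or equivalent per day within 12 weeks". It names neither grade 4 nor recurrence as a reason to stop.

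Two other places bear on the point. Table 5's last row, All Other Drug-Related Toxicity, permanently discontinues at grade 4. Table 7, for immune-related events not otherwise specified, puts grades 3 and 4 together under withholding, with discontinuation at the investigator's discretion or if steroids cannot be tapered.

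On precedence, Section 6 refers dose delays to its tables without ranking them. Section 6.1 opens with "Pembrolizumab must be withheld for drug-related toxicities and severe or life-threatening AEs as per the Table below". The Table 5 caption then sends the reader onward: "see more detailed recommendations for each event below the table".

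**The concern.** A grade 4 event whose steroids are tapered in time ends pembrolizumab under the table but is only a hold under the text. The caption presents the table as a summary and the text as the fuller guidance, so a clinician managing the event may well work from the text. This is a stopping rule for a possibly life-threatening immune toxicity, in a combination for which Section 13.5 says there are no safety data. What is at stake is patient safety and uniform dosing across sites in Arm A. No analysis depends on it.

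**Working it through.** **1. The rules side by side**

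| Event | Table 5 | Other Section 6.1 wording | Result |
|---|---|---|---|
| Hypophysitis, first grade 2 | Hold to grade 0-1 | Endocrine block: hold | Agree |
| Hypophysitis, first grade 3 | Hold, or stop at discretion | Endocrine block: hold | Compatible |
| Hypophysitis, grade 4 | Permanent stop | Endocrine block: hold; stop only if the steroid taper fails | Conflict |
| Hypophysitis, recurrent grade 2 or 3 | Permanent stop | Endocrine block: hold; recurrence not mentioned | Rule missing from the text |
| Other symptomatic endocrinopathy, grade 4 (e.g. adrenal insufficiency) | No row of its own; catch-all row: permanent stop | Endocrine block: hold | Conflict |
| Immune-related event not otherwise specified, grade 4 | Catch-all row: permanent stop | Table 7: withhold, stop at discretion or if the taper fails | Conflict |

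**2. Does the hold look deliberate?** Eight events with their own Table 5 row carry a permanent-stop grade: diarrhea/colitis, hepatic, hypophysitis, hyperthyroidism, infusion reaction, myocarditis, pneumonitis and renal. Seven of the eight repeat the stop in the guidance below the table; hypophysitis does not. In the same Endocrine section, "Grade 4 hyperthyroidism events" has a separate entry that discontinues the drug. Pneumonitis, the only other dedicated row with a recurrence stop, repeats it: "discontinue pembrolizumab if upon re-challenge the patient develops a second episode of Grade 2 or higher pneumonitis". This points to a drafting slip. The count covers dedicated rows only. The catch-all row is a ninth row with a grade 4 stop, and Table 7 does not carry that stop through either.

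**3. How often could it matter?** Inputs: 30 planned Arm A patients (Section 13.5), and grade 4 hypophysitis rates of 0.2% (n = 411) and 0.6% (n = 162) from Table 11. The assumption is that these rates apply to this population and regimen.

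- Expected cases = n × p: 30 × 0.002 = 0.06; 30 × 0.006 = 0.18.
- Chance of at least one = 1 − (1 − p)^30: 1 − 0.998^30 = 0.058; 1 − 0.994^30 = 0.165.
- Chance of none: 0.942 and 0.835.
- Patients behind each rate: 0.002 × 411 = 0.82; 0.006 × 162 = 0.97. Each is about one patient. The larger column includes the 2 mg/kg three-weekly schedule, so it may be the same patient.
- Exact 95% interval for 1/411: 0.006% to 1.35%, giving a 0.2% to 33% chance of at least one case in 30. For 1/162: 0.016% to 3.39%, giving 0.5% to 64%.

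The documents give no rate for recurrent hypophysitis, so no count is offered for it.

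**The case against.** The strongest reply is that Table 5 already governs. Section 6 points to the tables for delays, Section 6.1 makes withholding per the table mandatory, and the caption calls the text recommendations. The event text says hold but gives no permission to restart. The restart rule for hypophysitis is in Table 5, where the entry for grade 4 or recurrence is a permanent stop. Section 5.2.2 and Section 6 allow further doses only when the protocol's criteria are met.

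Much of this stands. A site that reads the table with the text will stop the drug, and one that follows Table 5 breaches nothing. A reader might infer that the protocol authorizes re-dosing after grade 4 hypophysitis. It does not: the text is silent on restarting. What remains is that the provisions on withholding and delay do not say which instruction prevails on a permanent stop. The remark before the event blocks that treatments are recommendations concerns the choice of agents.

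A reader might also infer a second contradiction on myocarditis, because Table 5 holds grade 1-2 until grade 0 while the pooled miscellaneous text withholds at grade 1 only if symptomatic treatment fails. The documents do not support giving this equal weight. It concerns a hold, which the opening of Section 6.1 ties to the table, and the text nowhere says to continue dosing. Nor does the instruction to manage steroid-treated grade 1-2 events as grade 3 imply a permanent stop, because the miscellaneous text sets the cardiac stop at grade 3 or higher.

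Detection is also good. Hypophysitis of grade 3 or above is reported to the Sponsor-Investigator within 24 hours, and Section 13.5 lists all grade 4 events for review.

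**Conclusion.** The inconsistency is real and specific. For grade 4 hypophysitis Table 5 and the event text give different instructions, and the same mismatch reaches grade 4 events in other symptomatic endocrinopathies and in Table 7. The recurrence rule is an omission from the text; calling it a contradiction would go too far, since nothing in the text permits treatment after a second episode.

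This is a minor patient-safety consistency correction. On the Table 11 rates the chance of any grade 4 hypophysitis among 30 Arm A patients is about 6% to 17%. That range is imprecise, because it rests on about one patient per column and on melanoma patients given pembrolizumab without radium-223. There is no effect on sample size, power or any endpoint.

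**What to change.** - Split the endocrine block. Keep the hold for first grade 2 and grade 3 events, leaving the grade 3 discretion as in Table 5. Permanently discontinue for grade 4 hypophysitis, for grade 4 of any other symptomatic endocrinopathy in the block, and for recurrent grade 2 or 3 hypophysitis.
- Give grade 4 its own row in Table 7, with a permanent stop to match Table 5's catch-all row.
- Add one sentence to Section 6.1: where table and text conflict on a hold or a permanent stop, Table 5 governs, including its All Other row. This also settles the grade 1 myocarditis hold. The sentence should not leave events without a dedicated row to the event text, because that would turn grade 4 adrenal insufficiency into a hold.
- In drafting that sentence, keep the stops that the event text sets more strictly than the catch-all row. The text discontinues at grade 3 for neurologic events and pericarditis, where the catch-all row only holds.
- Optional: say that managing grade 1-2 myocarditis as grade 3 refers to steroid treatment.

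The cost is protocol wording and a short site memo. Visits, procedures and patient numbers do not change.
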